#### 6.2 IMPORTANT PROTOCOL DEVIATIONS

Consistency check listings (for identification of deviations from time windows) and a list of protocol deviations (e.g. deviations in drug administration, in blood sampling times, etc.) will be provided to be discussed at the Report Planning Meeting (RPM). At this meeting, it will be decided whether a discrepant data value can be used in the analyses or whether it must be corrected in the clinical database. Each protocol deviation must be assessed to determine whether it is an important protocol deviation (iPD). For definition of iPDs, and for the process of identification of these, refer to the BI reference document "Identify and Manage Important Protocol Deviations (iPD)" (2).

If any iPDs are identified, they are to be summarised into categories and will be captured in the decision log. Categories which are considered to be iPDs in this trial are defined in the integrated quality and risk management plan (IQRMP). If the data show other iPDs, the definition in the IQRMP and the table below will be supplemented accordingly by the time of the RPM. Additionally, all iPDs will be documented in the DV sheet.

iPDs will be summarized and listed. Table 6.2: 1 specifies which kind of iPDs could potentially lead to exclusion from which analysis set (cf. Section 6.3). The decision on exclusion of subjects from analysis sets will be made at the latest at the RPM, after discussion of exceptional cases and implications for analyses.

TSAP for BI Trial No: 1371-0022 Page 13 of 24

Proprietary confidential information © 2021 Boehringer Ingelheim International GmbH or one or more of its affiliated companies

Table 6.2: 1 Handling of iPDs

iPD code	iPD Category & Brief Description	Excluded from which analysis set
A1	Inclusion criteria not met	PKS
A2	Exclusion criteria violated	PKS
B1	Informed consent not available/not done	TS, PKS
B2	Informed consent too late	None
C1	Incorrect trial medication taken	PKS
C2	Randomisation not followed	PKS
СЗ	Non-compliance	PKS
C4	Medication code broken inappropriately	PKS
C5	Incorrect intake of trial medication	PKS
C6	Improper washout between treatments	PKS
D1	Prohibited medication use	PKS
D2	Mandatory medication not taken	PKS
D3	Improper washout of concomitant medication	PKS
E1	Certain violations of procedures used to measure primary or secondary data	PKS
F1	Certain violations of time schedule used to measure primary or secondary data	PKS
G1	Incorrect intake of meal	PKS
H1	PDs affecting efficacy, safety and rights	TS, PKS

#### 6.3 SUBJECT SETS ANALYSED

Subject sets will be used as defined in the CTP, Section 7.3.

TSAP for BI Trial No: 1371-0022

Proprietary confidential information © 2021 Boehringer Ingelheim International GmbH or one or more of its affiliated companies

Table 6.3: 1 Subject sets analyzed

	Subject set	
Class of endpoint	TS	PKS
Disposition	X	
iPDs	X	
Primary PK endpoint		X
Secondary PK endpoint		X
Safety parameters & treatment exposure	X	
Demographic/baseline endpoints	X	

#### 6.4 SUBGROUPS

A subgroup analysis is not planned.

#### 6.5 POOLING OF CENTRES

This section is not applicable, because the study was performed in only one centre.

#### 6.6 HANDLING OF MISSING DATA AND OUTLIERS

Data of screened subjects who were withdrawn from the trial prior to first administration of any study drug will not be reported in the CTR.

Data of subjects who failed to complete all periods of the study (dropouts or withdrawals) will be reported in the CTR as far as their data are available. All withdrawals will be documented and the reason for withdrawal reported in the CTR.

**CTP Section 7.5.1**: *It is not planned to impute missing values for safety parameters.* 

One exception where imputation might be necessary for safety evaluation are AE dates. Missing or incomplete AE dates are imputed according to BI standards (3).

Missing data and outliers of PK data are handled according to BI standards (4) and (5). CTP Section 7.5.2: Pharmacokinetic parameters that cannot be reasonably calculated based on the available drug concentration-time data will not be imputed.

#### 6.7 BASELINE, TIME WINDOWS AND CALCULATED VISITS

Baseline is defined as the last available value before any administration of BI 894416 (in any formulation).

Time windows are defined in Section 6.1 of the CTP. Adherence to time windows will be checked at the RPM.

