Statistical methods	Preliminary pharmacokinetic analyses and simulations will be performed between trial part 1 and trial part 2A as, well as between part 2A and 2B, if appropriate. Relative bioavailability will be estimated by the ratios of the geometric means (test/reference) for primary, secondary and further selected endpoints. Additionally, their two-sided 90% confidence intervals (CIs) will be provided. This method corresponds to the two one-sided t-test procedure, each at a 5% significance level. Since the main focus is on estimation and not testing, a formal hypothesis test and associated acceptance range is not specified. The statistical model will be an analysis of variance (ANOVA) on the logarithmic scale. CIs will be calculated based on the residual error from the ANOVA. Descriptive statistics will be calculated for all endpoints.

FLOW CHART – TRIAL PART 1

Period	Visit	Day	Planned time (relative to drug administration) [h:min]	Approximate clock time of actual day [h:min]	Event and comment	Safety laboratory ⁷	PK blood	Neurological examination ⁸	12-lead ECG	Vital signs (BP, PR)	Questioning for AEs and concomitant therapy ⁶
SCR	1	-28 to -1			Screening (SCR) ¹	A		x	x	x	
1/2/3/4/5/6 (six periods separated by a wash-out of at least 4 days)	2/3/4/5/6/7	-1	-12:00	20:00	Admission to trial site (visit 2 only)	x ⁵					x
			-11:30	20:30	Snack (voluntary)						
		1	-1:30	06:30	Allocation to treatment ² (visit 2 only)	B ^{2/9}	x ²		x ²	x ²	x ²
			-0:30	07:30	High fat, high calorie breakfast (Treatment T5 & T6 only)						
			0:00	08:00	Drug administration (with 240 mL fluid intake)						
			0:20	08:20			x				x
			0:40	08:40			x				x
			1:00	09:00			x		x	x	x
			2:00	10:00	240 mL fluid intake		x		x	x	x
			3:00	11:00			x				x
			4:00	12:00	240 mL fluid intake, thereafter lunch ³		x		x	x	x
			5:00	13:00			x				x
			6:00	14:00			x				x
			8:00	16:00	Snack (voluntary) ³		x		x	x	x
			10:00	18:00			x				x
			11:00	19:00	Dinner						
			12:00	20:00			x				x
			14:00	22:00			x				x
			16:00	24:00			x				x
		2	24:00	08:00		B	x		x	x	x
			34:00	18:00			x				x
		3	48:00	08:00			x				x
			58:00	18:00			x				x
		4	72:00	08:00	Breakfast (voluntary) Discharge from trial site (visit 7 only)	B ¹⁰	x		x	x	x
EoT	8	8 to 15			End of trial (EoT) examination ⁴	A		x	x	x	x

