Trial part 2B (only one, either H or K will be tested in the fasted and fed state)

- T9- Prototype Formulation H or K : 50-75 mg BI 894416, fasted (n=18)
- T10- Prototype Formulation H or K : 50-75 mg BI 894416, after high-fat, high-calorie breakfast (n=18)

For details on decision making and procedures between trial parts, refer to Section [6.2.2](#).

Proprietary confidential information © 2020 Boehringer Ingelheim International GmbH or one or more of its affiliated companies

There will be a washout period of at least 4 days between the treatments, i.e. the dose in the preceding treatment period and the dose in the following treatment period are separated by at least 4 days.

Subjects will be randomly allocated to the different treatment sequences. For details, refer to Section [4.1](#).

An overview of all relevant trial activities is provided in the [Flow Chart](#). For visit schedule and details of trial procedures at selected visits, refer to Sections [6.1](#) and [6.2](#), respectively.

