5.3.2 Methods of sample collection

5.3.2.1 Blood sampling for pharmacokinetic analysis

BI 894416

For quantification of BI 894416 concentrations in plasma, approximately 2.0 mL of blood will be drawn from an antecubital or forearm vein into a [REDACTED] blood drawing tube at the times indicated in the [Flow Chart](#). Blood will be withdrawn by means of either an indwelling venous catheter or by venepuncture with a metal needle.

[figure not shown]

At a minimum, the sample tube labels should list BI trial number, subject number, visit, and planned sampling time. Further information such as matrix may also be provided.

Further use of samples

After the completion of BI 894416-quantification in plasma aliquots, the left-over and/ or back-up aliquots may be used for further methodological investigations (e.g. for stability testing or assessment of metabolites. However, only data related to the analyte and/ or its metabolite(s), including anti-drug antibodies (if applicable), will be generated by these additional investigations. The study samples will be discarded after completion of the additional investigations but not later than 5 years after the CTR is archived.

Results of any further investigations are not planned to be part of the CTR but can be included into the CTR, if necessary.

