7.3.4 Safety analyses

Safety will be analysed based on the assessments described in Section [2.2.2.2](#). All treated subjects (TS, refer to Section [7.2](#)) will be included in the safety analysis. Safety analyses will be descriptive in nature and based on BI standards. No statistical comparison between treatment groups for safety data is planned, unless otherwise specified within the relevant section.

For all analyses, the treatment actually administered (= treatment at onset) to the subject will be used (any deviations from the randomised treatment will be discussed in the minutes of the Report Planning Meeting).

Treatments will be compared in a descriptive way. Tabulations of frequencies/ proportions will be used to evaluate categorical (qualitative) data, and tabulations of descriptive statistics will be used to analyse continuous (quantitative) data.

Measurements (such as ECG, vital signs, or laboratory parameters) or AEs will be assigned to treatments (refer to Section [4.1](#)) based on the actual treatment at the planned time of the measurement or on the recorded time of AE onset (concept of treatment emergent AEs). Therefore, measurements planned or AEs recorded prior to first intake of trial medication will be assigned to the screening period, those between first trial medication intake and end of REP (refer to Section [1.2.3](#)) will be assigned to the treatment period. Events occurring after the REP but prior to next intake or end of trial termination date will be assigned to 'follow-up'. In case of two or more treatments, the follow-up will be summarized according to the previous treatment. These assignments including the corresponding time intervals will be defined in detail in the TSAP. Note that AEs occurring after the last per protocol contact but entered before final database lock will be reported to Pharmacovigilance only and will not be captured in the trial database.

Additionally, further treatment intervals (analysing treatments) may be defined in the TSAP in order to provide summary statistics for time intervals, such as combined treatments, on-treatment totals, or periods without treatment effects (such as screening and follow-up intervals).

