#### 6. GENERAL ANALYSIS DEFINITIONS

#### 6.1 TREATMENTS

For basic study information on treatments to be administered, assignment of treatment groups, and selection of doses, cf. Section 4 of the CTP.

The trial is divided into two parts but only trial part 1 was performed.

In **trial part 1**, each subject is planned to be treated in five subsequent treatment periods (five-period cross-over) with one single dose in each treatment period followed by one single dose in a sixth treatment period in a fixed sequence.

Treatments in the five-period cross-over:

- Reference treatment 1 (R1) 60mg tab IR fasted: 60 mg of BI 894416, IR tablets under fasted conditions
- Test treatment 1 (T1) 62.5mg tab FRR fasted:
   62.5 mg of BI 894416, ER tablet (fast release rate) under fasted conditions
- Test treatment 2 (T2) 62.5mg tab SRR fasted:
   62.5 mg of BI 894416, ER tablet (slow release rate) under fasted conditions
- Test treatment 3 (T3) 62.5mg cap FRR fasted:
   62.5 mg of BI 894416, ER capsule (fast release rate) under fasted conditions
- Test treatment 4 (T4) 62.5mg cap SRR fasted:
   62.5 mg of BI 894416, ER capsule (slow release rate) under fasted conditions

Each subject is planned to be randomly allocated to one of five treatment sequences (T3-R1-T1-T4-T2, T2-T1-T3-R1-T4, T4-T3-R1-T2-T1, T1-T4-T2-T3-R1 and R1-T2-T4-T1-T3, cf. Table 6.1: 2).

Treatments in the fixed sequence:

- Test treatment 5 (T5) 62.5mg tab SRR fed:
   62.5 mg of BI 894416 ER, tablet (slow release rate) after a high fat breakfast
- Test treatment 6 (T6) 62.5mg cap SRR fed:
   62.5 mg BI 894416, capsule (slow release rate) after a high fat breakfast

Subject will be randomly allocated to either T5 or T6, stratified by sequence (cf. Table 6.1: 2 for an overview of the treatment sequences).

For statistical analysis of AEs, safety laboratory data and vital signs, the following analysis phases are defined for each subject:

Table 6.1: 1 Flow chart of analysis phases for statistical analyses of AEs

Study analysis phase	Label	Start (inclusive)	End (exclusive)
Screening	Screening	Date of informed consent	Date/time of administration of BI 894416 in any formulation
On-treatment	BI 894416 respectively	Date/time of administration of BI 894416 in any formulation	Date/time of administration of BI 894416 in another formulation or 12:00 a.m. on day after subject's trial termination date, whichever occurs earlier

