#### 7.8.2 Laboratory data

The analyses of laboratory data will be descriptive in nature and will be based on BI standards "Display and Analysis of Laboratory Data" (9).

Analyses will be based on normalised values, which mean transforming to a standard unit and a standard reference range. The original values will be analysed if the transformation into standard unit is not possible for a parameter.

Descriptive statistics of absolute values and change from baseline from laboratory parameters over time (see Section 6.7) will be provided. Frequency tables of changes between baseline and last value on treatment with respect to the reference range will be presented.

Unscheduled measurements of laboratory data will be assumed to be repeat measurements of the most recent scheduled measurement (e.g. for follow-up or confirmation of a particular value). Therefore, unscheduled measurements will be assigned to the planned time point of the previous scheduled measurement. Descriptive statistics will be calculated by planned time point based on the worst value of the subject at that planned time point (or assigned to that planned time point).

Possibly clinically significant abnormal laboratory values are only those identified either in the Investigator's comments or at the RPM at the latest. It is the Investigator's responsibility to decide whether a lab value is clinically significant abnormal or not. Standard or project-specific rules for flagging clinically significant values in an automated manner will not be applied in this study.

Clinically relevant findings in laboratory data will be reported as baseline conditions (prior to first administration of study treatment) or as AEs (after first administration of study treatment) if judged clinically relevant by the investigator, and will be analyzed as such.

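### One pre-first-dose baseline serves all six periods, so laboratory and vital-sign changes after doses 2 to 6 mix time in-house and blood loss with the response to that dose; a within-period baseline is a cheap, minor addition

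*SAP*

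**What the plan says.** SAP 6.7 sets the reference: "Baseline is defined as the last available value before any administration of BI 894416 (in any formulation"). In practice this is the value before the period-1 dose.

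SAP Table 6.1: 1 is consistent with that. The screening phase ends at "Date/time of administration of BI 894416 in any formulation", and each on-treatment phase runs until the next formulation is given. The table title names only AEs, but the sentence introducing it also covers safety laboratory data and vital signs. On that reading the pre-dose values of periods 2 to 6 fall in the previous formulation's on-treatment phase.

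SAP 7.8.2 plans "Descriptive statistics of absolute values and change from baseline from laboratory parameters over time", and SAP 7.8.3 plans the same for vital signs. SAP 6.1 puts both data types in a single BI 894416 column. SAP 7.8.4 handles ECG through clinically relevant findings only.

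In the protocol, the part 1 flow chart has "six periods separated by a wash-out of at least 4 days". Its -1:30 row on Day 1 lists laboratory set B, ECG and vital signs, to be completed within 3 h before dosing. Protocol 7.3.4 says "Treatments will be compared in a descriptive way" and asks for changes from baseline in laboratory data and vital signs. It gives no other definition of baseline for these tables.

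**The concern.** In a single-dose crossover, the safety question is what changes after each dose. With one remote baseline, a change in period 3, say, is the sum of two parts: what drifted between the first dose and the third, and what the third dose did. Subjects remain in the unit throughout part 1 (protocol 6.2.2; the flow chart discharges them at visit 7 only) and are bled repeatedly. Drift in haemoglobin, haematocrit or red cells is therefore plausible without any drug effect, and a confinement effect on pulse or blood pressure is possible.

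Period 6 deserves most attention. It contains only T5 and T6, both fed. If the summaries over time are laid out by visit, pooling does not dilute anything in those rows: fed dosing, the longest stay and the largest blood loss all coincide. A reader could take drift for a response to fed dosing, or dismiss a real acute shift of similar size as drift.

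**Working it through.** The plan gives no figure to reproduce, and the sample size is not based on a power calculation, so only elapsed time and blood volume need checking.

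**Inputs**
- Six periods, with washout defined dose to dose: "the dose in the preceding treatment period and the dose in the following treatment period are separated by at least 4 days" (protocol 3.1).
- PK blood: "approximately 2.0 mL of blood will be drawn" per sample (protocol 5.3.2.1).
- PK samples per period, counted in the part 1 flow chart: 1 pre-dose, 2 before 1 h, 6 from 1 to 6 h, 5 from 8 to 16 h, and 5 from 24 to 72 h. Total 1 + 2 + 6 + 5 + 5 = 19.
- Whole-study blood cap of 500 mL (protocol 1.4.2). Safety-tube volumes are not stated.

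**Formulas for dose p**
- Minimum days since baseline = (p - 1) x 4.
- PK blood from earlier periods = (p - 1) x 19 x 2.0 mL = (p - 1) x 38 mL.
- Illustrative haemoglobin fall = 15 x V / 5000 g/dL, with V the blood drawn in mL. This assumes 15 g/dL, 5 L blood volume and no red-cell regeneration. None of these comes from the documents, and without regeneration the result is an upper bound for the volume used.

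| Dose | Minimum days | Earlier PK blood (mL) | Haemoglobin, upper bound (g/dL) |
|---|---|---|---|
| 2 | 4 | 38 | 0.11 |
| 3 | 8 | 76 | 0.23 |
| 4 | 12 | 114 | 0.34 |
| 5 | 16 | 152 | 0.46 |
| 6 | 20 | 190 | 0.57 |

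If safety tubes raised the total before dose 6 to 300 mL (also an assumption), the last entry would be 15 x 300 / 5000 = 0.90 g/dL. PK blood over six periods is 6 x 38 = 228 mL, inside the cap. The minimum stay is 0.5 + 20 + 3 = 23.5 days.

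**Balance across treatments.** In the five sequences of protocol 3.1, R1 and T1 to T4 each appear once in every one of periods 1 to 5. The minimum lags are 0, 4, 8, 12 and 16 days for each, with mean 40 / 5 = 8 days. The 24 subjects cannot be split equally over 10 sequences (24 / 10 = 2.4), so the balance is approximate. T5 and T6 are always at 20 days or more.

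**With a within-period baseline.** The gap from baseline to dose is at most 3 h in every period. The earlier-period blood drops out, leaving at most the same period's 38 mL (15 x 38 / 5000 = 0.11 g/dL on the same assumptions).

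**The case against.** The strongest reply is that no planned table is biased between treatments. SAP 6.1 pools laboratory and vital-sign data in one column. A reader might infer that change tables by formulation will show spurious fed effects for T5 and T6, or unequal drift for R1 and T1 to T4. The documents do not support that: no such tables are planned, and the five fasted treatments are roughly balanced over periods 1 to 5. This part of the reply stands. What remains is the by-visit layout, where the period-6 rows are fed-only even in a pooled column. The SAP says changes are shown over time but does not spell out that layout.

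Second, much can be recovered. Absolute values are also summarised, and individual values are listed (SAP 7). If planned time points are kept by period, and the same subjects contribute to both, the post-dose mean minus the pre-dose mean of that period equals the mean within-period change. This stands for means. The standard deviations of the paired changes cannot be obtained that way and would have to be rebuilt from the listings.

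Third, a drug-naive reference is a defensible choice. Every period gives the same compound, the protocol prescribes no other baseline, and a period baseline could absorb a lasting effect of an earlier dose. This also stands. It is a reason to keep the present baseline alongside a second one, not a reason to omit the second.

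Fourth, little depends on these tables. Clinical relevance is judged by the investigator and reported as AEs, not derived from change from baseline. That is why the point is minor.

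**Conclusion.** The point holds as a minor improvement. SAP 6.7 is not an error and does not contradict the protocol. It does mean that the descriptive laboratory and vital-sign changes after doses 2 to 6 include at least 4 to 20 days in-house and about 38 to 190 mL of earlier PK blood, as well as the response to that dose.

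Three stronger readings should be resisted. The 20-day minimum applies to the sixth dose only; for doses 2 to 5 it is 4 to 16 days. The haemoglobin figures are upper bounds on outside assumptions, not expected drift, and the documents give no figure for a confinement effect on pulse or blood pressure. ECG is not affected, because no ECG change table is planned; nor are the primary and secondary PK endpoints.

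The conclusion rests on two readings. One is that the -1:30 flow-chart row applies to all six periods, with the visit-2 restriction belonging to the allocation event alone. The other is that the analysis phases in Table 6.1: 1 cover laboratory and vital-sign data, as their introductory sentence says. The period-6 remark also assumes display by visit.

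**What to change.** - In SAP 6.7, 7.8.2 and 7.8.3, add change from the last value before the dose of the same treatment period, for laboratory and vital-sign data.
- In Table 6.1: 1, assign that pre-dose value to the new period instead of to the previous formulation's on-treatment phase.
- Summarise this within-period change by treatment, in line with protocol 7.3.4, and amend the single-column rule in SAP 6.1 to allow it. Without this step the new baseline would still not show what follows each formulation.
- Keep the pre-first-dose baseline for cumulative change and for end of trial, including the laboratory shift table to the last on-treatment value. It covers the one drawback of the period baseline, a lasting effect of an earlier dose.

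The cost is SAP wording and programming. SAP 4 states that part 1 has been performed, and the values needed were already scheduled. One limit remains: fed dosing occurs only in period 6, so a fed-versus-fasted comparison of within-period changes is free of drift accumulated before the dose but still cannot be separated from period.
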